Data on initial set tidal volume in the ED and ICU across Intermountain Healthcare hospitals shows variability in compliance with lung protective ventilation—as represented by numbers of patients in different categories of initial set tidal volume measured in ml/kg PBW (**Figure 1, Table 1, and Figure 3** *in the Supporting Documents section*). These data include all patients who had initiation of mechanical ventilation in the ED or ICU with volume control ventilation and without a spontaneous breathing mode, such as pressure support or continuous positive airway pressure, at Intermountain Healthcare hospitals in 2014 (Intermountain Medical Center, McKay Dee Hospital, LDS Hospital, Utah Valley Regional Medical Center, Park City, American Fork, Riverton, Alta View, Logan, Valley View, and Dixie Regional Medical Center). Results from this

investigation demonstrated that only 20% of initial tidal volume settings in the ED and ICU were ≤6.0 ml/kg PBW (**Figure 1**), 50% of patients in the ED and 57% of patients in the ICU had initial tidal volume settings of ≤7.0 ml/kg PBW and 22% of ED patients and 18% of ICU patients had initial tidal volume settings >8 ml/kg PBW. This represents about one in five patients who were ventilated with high tidal volumes that may injure the lung. There was no initial determination of whether patients had ARDS in the data set.

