Systemic Early neuromuscular blockade (ROSE)" from the NIH/NHLBI Prevention and Early Treatment of Acute Lung Injury (PETAL) Network will use a high PEEP strategy for moderate to severe ARDS based on the ARDS Network High PEEP protocol (**Table 2**). Intermountain Healthcare leads the Utah Clinical Center of the PETAL Network, and the high PEEP protocol that will be computerized in iCentra matches the PETAL Network high PEEP protocol for ROSE.

Based on current evidence, a lung protective ventilation strategy using the ARDS Network ventilation protocol with a target tidal volume of 6 ml/kg PBW is an accepted standard for all intubated patients at Intermountain Healthcare EDs and ICUs. Plans for implementation of the ARDS Network 6 ml/kg ventilation protocol into iCentra were made as an initiative to standardize care for mechanical ventilation across Intermountain Healthcare Hospitals. Lung protective ventilation has the potential to benefit patients who require mechanical ventilation for neurologic problems, surgery, drug overdose, or airway protection as well as hypoxemic respiratory failure.

[figure not shown]

Table 1. Numbers of patients in initial tidal volume ranges in the ED and ICU

		>4	>5	>6	>7	>8	>9	>10	>11	>12	>13
		and	and	and	and	and	and	and	and	and	and ≤
	≤ 4	≤ 5	≤ 6	≤ 7	≤ 8	≤ 9	≤ 10	≤ 11	≤ 12	≤ 13	16
ED	3	14	191	322	289	174	40	14	0	2	4
ICU	5	13	377	721	480	233	71	31	7	4	2

Figure 2. Compliance with High PEEP Strategy in ARDS Network 2 Studies EDEN¹⁸, OMEGA¹⁹, and SAILS.²⁰

EDEN/OMEGA/SAILS enrollment values black line is high-PEEP (ROSE) compliant

[figure not shown]

Table 2. Comparison of High and Low PEEP Strategies

	FIO2 0.3	FIO2 0.4	FIO2 0.5	FIO2 0.6	FIO2 0.7	FIO2 0.8	FIO2 0.9	FIO2 1.0
ROSE High PEEP	5	5-16	16-20	20	20	20-22	22	22-24
ALVEOLI High PEEP ¹⁴	5-14	14-16	16-20	20	20	20-22	22	22-24
ALVEOLI Low PEEP ¹⁴	5	5-8	8-10	10	10-14	14	14-18	18-24

Research Subjects:

Inclusion Criteria

- 1. Initiation of mechanical ventilation in the emergency department or intensive care unit at an Intermountain Healthcare hospital
- 2. Age ≥ 18 years

Exclusion Criteria

- Transition to comfort care in the emergency department or on the same day of admission to the ICU
- 2. Death on the same day of admission to the emergency department or ICU

Patient Selection

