Those to be enrolled must have respiratory failure requiring intubation and initiation of mechanical ventilation. Patients will be divided into two different groups: those patients who are managed with the computerized lung protective ventilation protocol as ordered by the attending physician and those patients managed with physician specified mechanical ventilation settings.

Compensation

Subjects will not be compensated for participating in this study.

Sample Size

The minimum sufficient sample size to detect a significant change in VFD was computed across a range of effects and heterogeneity. We estimate about 3,900 subjects would be sufficient to detect a 1.5-day increase in mean VFD with 80% power (*ICC* = 0.10) from a baseline of 21.9 VFD (SD=7.8) with a one-tailed test (**Table 3**).

Table 3. Minimum sample size for increase in mean VFD

ICC	1 day	1.5	2 day
		day	
0.01	6,800	3,200	2,300
0.10	8,500	3,900	2,300
0.20	8,300	4,000	2,400

The baseline VFD data for the power analysis was based on reported data from a meta-analysis of the association between tidal volume size and sedation needs

in patients without ARDS²⁵ among those who received initial tidal volumes between 6 and 10 ml/kg PBW – a demographic representative of our study population. The power analyses accounted for expected imbalance of patient enrollment (**Table 4**),^{26,27} heterogeneity among clusters,²⁸ and allowed for a variety of time effects (**Equation 1**).²⁹ This avoided artificial inflation of power at the study design stage.³⁰

The VFD y_{ikt} for each patient were simulated via a linear equation adapted from Hussy *et al.*³¹ with the addition of quadratic time effects:

$$y_{ikt} = \mu + \alpha_k + \beta_1 t + \beta_2 t^2 + \theta x_{ikt} + e_{ikt},$$
 (1)

where μ and e_{ikt} , were derived from the distribution of VFD reported in the metaanalysis by Serpa Neto *et al.*²⁵, θ varied from 1 to 2 per [name]'s instructions, α_k are the hospital-level random intercepts, $\beta = (\beta_1, \beta_2)$ is a vector of quadratic time effects, x_{ikt} is the initial tidal volume size for the *i*th subject in the *k*th cluster at time *t*.

	Volume	Proportion
McKay-Dee	542	0.1584
Utah Valley	608	0.1778
American Fork	68	0.0199
Dixie	479	0.14
Valley View	60	0.0175
IMC	1409	0.4119
LDS	206	0.0602
Riverton	49	0.0143

Table 4. Volume of mechanically ventilated patients in 2014

Methods/Procedures:

Research Strategy for Specific Aims 1 and 2

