Lung protective ventilation management using the computerized ARDS Network 6 ml/kg PBW ventilation protocol will be phased in among 11 Intermountain Healthcare hospitals in the manner of a phased implementation design synchronized with the rollout of iCentra. This is a quality improvement initiative to introduce a best practices ventilation protocol across Intermountain Healthcare hospitals and we request waiver of informed consent from the Institutional

Review Board in order to measure the effect on clinical outcomes and change in practice associated with this implementation. With each successive hospital that transitions to iCentra, [name] will provide educational presentations to the medical staff that manage mechanically ventilated patients. [name] and [name], a respiratory therapist, will also educate the respiratory therapists at each hospital in the computerized ARDS Network ventilation protocol. [name] will be available for phone consultation from physicians and respiratory therapists for real time assistance in utilizing the mechanical ventilation protocols.

The primary outcome is ventilator free days (VFDs) to day 28. We will use the same definition for liberation from mechanical ventilation as used in ARDS Network studies^{2,14} and in the proposed ROSE study from the NIH/NHLBI PETAL Network. Initiation of ventilator free days begins with two ventilator free days once unassisted breathing is present for 48 hours. Unassisted breathing is defined as²²:

- a. Extubated with face mask, nasal prong oxygen, or room air, OR
- b. T-tube breathing, OR
- c. Tracheostomy mask breathing, OR
- d. CPAP ≤ 5 without PS or IMV assistance
- e. Use of CPAP or BIPAP solely for sleep apnea management
- f. Use of a high flow oxygen system

Research Strategy for Specific Aim 3

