- The risk of this study is a potential loss of confidentiality. The study involves no more than minimal risk to the subject, as the study is observational only and the study will not alter the care that enrolled subjects receive. The computerized lung protective mechanical ventilation protocol will be available to clinicians as an order in iCentra, but will not be required.
- The sample size required to detect a significant change in VFD is estimated to be about 3,900 subjects. Including only the data for which consent can be obtained would prevent accurate conclusions from being drawn.
 Consequently, the research could not practicably be carried out without a waiver of consent.

Waiver of Authorization

PHI will be collected as a part of this study. The PHI will be used only for study purposes and will not be reused or disclosed except as required by law. The information obtained from medical records will be kept separate from clinical records.

All digital study records will be kept within the Intermountain Healthcare firewall in a location that is only accessible to authorized members of the study team. All paper study records will be maintained on a floor with secure badge access that only the research team can access.

After the study is complete, study identifiers will be removed from the dataset.

The data to be collected is detailed below. In particular, the dates to be collected are important for evaluating the primary outcome of interest, VFDs to 28 days.

Data Collection:

Data Elements Extracted from the EDW for the Mechanical Ventilation Study

- Region
- Hospital
- Facility ID
- Account Number
- EMPI
- Admit Date
- Discharge Date
- Admit Year
- Age
- Gender
- ICD Diagnosis code
- ICD Diagnosis description
- ICD Diagnosis long description
- ICU Stay
- Length of Stay(Days)
- Mortality Indicator
- Patient Type(inpatient(I) vs outpatient(O))
- Patient Type(Detailed code)
- Patient Type Description
- Death Location
- Discharge Disposition Description
- Discharge Reason(same as above)
- ED Admit Date
- ED Discharge Date
- Total Cost
- Ventilator Location(First Vent Check Location)
- First Date of Ventilator Check
- Ventilator Mode
- First Date of Ventilator Check
- Intubation Date
- Intubation Location(Same as Ventilator Location)
- Room Trace(It is more detailed than the ones above)
- In Hospital Mortality

- Ventilator Mode
- Machine Corrected Volume
- Set Tidal Volume
- Spontaneous Volume
- Height
- Predicted Body Weight

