- Tidal Volume per Predicted Body Weight
- Measured Volume per Predicted Body Weight
- Difference between Tidal Volume per PBW and Measured Volume per PBW
- Difference between admission date and death date
- 30 Day Mortality
- 60 Day Mortality
- 90 Day Mortality
- Initial Arterial Blood Gas recorded during hospital stay
- PaO2 (measured)
- PaO2 (corrected)
- FiO2
- PaO2 / FiO2

Data Analysis:

Primary Outcomes

The primary outcome will be VFD to day 28. Patients who experience death within 28 days of ICU admission will be counted as having zero VFD.

Secondary outcomes will include: hospital discharge disposition; hospital, 30-day, and 90-day mortality; time to first ICU activity; hospital, ICU length of stay; protocol compliance; implementation of a high PEEP strategy in patients with PaO_2/FIO_2 ratios \leq 200; heath care utilization; quality of life (SF-36 or similar); and costs of care.

Data Analysis

Descriptive analyses will include Fisher's exact test and Pearson's chi-square test for comparing pairs of binomially distributed variables with and without sparse cells, respectively. Wilcoxon rank sum test, a nonparametric analogue of Student's *t* test, will be used to compare non-Gaussian, continuous distributions. Bootstrapped Kolmogorov-Smirnov (K-S) test will compare distributions of

ordinal, discrete data. The bootstrapped K-S test is able to handle instances in which many ties are present between distributions.²⁴

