Generalized linear mixed models (GLMM) with hospital-level random intercepts and an identify link function will be used to measure the effect of initial tidal volume size on VFD. It is proposed to measure the treatment as a continuous variable (rather than as a dichotomous indicator of whether the mechanically ventilated patient was cared for at a post-intervention site) in order to account for the variable "usual care" practices of tidal volume size. The protocol will be phased sequentially in a non-randomized phased implementation manner. Since it is hypothesized that the bundle will improve care and, resultantly, decrease duration of time on ventilator, statistical significance will be determined by a one-tailed, 5% significance test. Heterogeneity among clusters will also be measured and accounted for random intercepts. Potential secular trends will be adjusted for by inclusion of quadratic time effects, which would capture a variety of time effects – from linear to bell-shaped. Patient-specific confounders will be controlled for by additive inclusion of a matrix of patient-level covariates.

Mitigation Plans and Interim Analysis

We plan an interim analysis for futility and efficacy at the end of the third step, following the successful phasing in of the second cluster. If the mean VFD following implementation of the bundle is equivalent to the mean VFD prior to implementation (according to the two one-sided test procedure with 99% confidence having an equivalence margin of four hours) then futility will be declared and further data collection will cease. Conversely, if the mean VFD following implementation has increased by more than 2 days (according to a one-sided hypothesis test with 99% confidence), efficacy will have been established and further data collection will also cease.

Data Sharing:

Development of the ventilation protocol in iCentra for mechanical ventilation will likely increase the number of VFDs, decrease healthcare utilization and decrease cost. To ensure that the proposal deliverables are met, we have designed the following dissemination plan:

Internal Strategic Planning

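### The zero-VFD death rule runs from ICU admission, but cohort entry and exposure are fixed at the start of ventilation, and day 0 of the VFD count is not stated

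*Protocol*

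**What the plan says.** Four statements in the protocol bear on the clock of the primary outcome.

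- **Entry.** Inclusion criterion 1 is "Initiation of mechanical ventilation in the emergency department or intensive care unit at an Intermountain Healthcare hospital". Patient Selection repeats it: "Those to be enrolled must have respiratory failure requiring intubation and initiation of mechanical ventilation".
- **Exposure.** Under Data Analysis, mixed models "will be used to measure the effect of initial tidal volume size on VFD". The exposure is therefore set at the same moment as entry.
- **Horizon.** Research Strategy for Specific Aims 1 and 2 says "The primary outcome is ventilator free days (VFDs) to day 28". It then defines unassisted breathing and the 48-hour rule for liberation. It does not name the event that is day 0.
- **Death rule.** Primary Outcomes says "Patients who experience death within 28 days of ICU admission will be counted as having zero VFD".

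The exclusion criteria remove deaths, and transitions to comfort care, only when they fall on the first day. The extraction list under Data Collection includes the intubation date and "First Date of Ventilator Check". It times death by the difference between the admission date and the death date.

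**The concern.** Entry and exposure share one time zero, the start of ventilation. The death component of the primary outcome is given another, ICU admission. The two can differ in both directions: a patient may be ventilated in the ED before reaching the ICU, or intubated days after ICU admission. The Study Timeline section also foresees ventilation begun before transfer to a tertiary hospital, which can separate the two events further.

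At stake is the scoring of the primary outcome. Death sets a patient to zero, so whether a late death falls inside the window can change that patient's value by many days. If the window does not start at entry, patients also differ in how many VFDs they could attain, for reasons unrelated to how they fared on the ventilator.

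**Working it through.** **How common are both entry routes?** From Table 1 (2014):

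- ED: 3+14+191+322+289+174+40+14+0+2+4 = 1,053
- ICU: 5+13+377+721+480+233+71+31+7+4+2 = 1,944
- ED share: 1,053/2,997 = 35.1%

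The same counts reproduce the plan's percentages above 8 ml/kg: 234/1,053 = 22.2% in the ED and 348/1,944 = 17.9% in the ICU.

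**Where does the death window end?** Let L be days from ICU admission to the start of ventilation. The rule then reaches ventilation day 28 − L.

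| L | Rule ends on ventilation day |
|---|---|
| −1 (ventilated in the ED a day before ICU admission) | 29 |
| 0 | 28 |
| 3 | 25 |
| 7 | 21 |
| 10 | 18 |

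**Case A: VFDs run from the start of ventilation.** The two windows differ unless L = 0. Example with assumed dates: ventilated on ICU day 10, liberated on day 14, dead on day 30. Death falls on ventilation day 20, yet the rule does not set VFD to zero. Conversely, a patient with L = −1 who dies on ICU day 28 is set to zero although alive on ventilation day 28.

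**Case B: VFDs run from ICU admission.** The windows agree and no death is mis-scored. But a patient ventilated L days after ICU admission has only 28 − L days in which to accrue VFDs, and the window starts at an event other than entry.

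**Either case.** An ED-ventilated patient who survives the first day and dies later without an ICU admission stays in the cohort and has no origin for the rule.

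**Size in case A (assumptions).** The documents give no distribution of L. Let f be the share ventilated late, h the daily death risk near day 28, and t the hours by which ED ventilation precedes ICU admission. In 4,000 patients:

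- Late-ventilated, 4,000·f·L·h: 4,000×0.15×3×0.002 = 3.6. Low: 4,000×0.05×1×0.001 = 0.2. High: 4,000×0.30×7×0.005 = 42.
- ED, 4,000×0.351×(t/24)×h: 0.7 with t = 6 and h = 0.002; 0.1 with t = 2 and h = 0.001; 3.5 with t = 12 and h = 0.005.
- Both together: about 4.3 (0.3 to 46), or 0.1% (up to about 1.1%).

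At an assumed 16 VFDs per mis-scored death, the late-ventilated group moves the overall mean by 3.6×16/4,000 = 0.014 day (high: 42×16/4,000 = 0.17). The design effect is 1.5 days.

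**Size in case B (upper bound).** If every late-ventilated patient survived and was liberated by day 28, the overall mean would fall by f·L = 0.15×3 = 0.45 day (0.05 to 2.1). This is a shift in level. It reaches the estimated effect only as far as lag is related to tidal volume or to period.

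**Does it bias the slope?** The only link in the documents is the ED/ICU difference in Table 1. Bin midpoints (lowest bin taken as 3.5, highest as 14.5) give means of 7.10 and 6.98 ml/kg, a difference d = 0.114, with variance V = 1.61. With p = 0.351, the slope bias is p(1−p)·d·(ED error − ICU error)/V.

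- Case A: the ICU error is 3.6×16/(4,000×0.649) = +0.0222 and the ED error is −0.008. The bias is 0.228×0.114×(−0.0302)/1.61 = −0.0005 day per ml/kg (−0.00004 to −0.005).
- Case B: the ICU error is −0.45/0.649 = −0.69 and the ED error is +0.25. The bias is 0.228×0.114×0.944/1.61 = +0.015 at most (0.003 to 0.06).

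The signs are opposite, and both are small against the simulated effects of 1 to 2 days.

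**The case against.** The best defence is that ICU admission is the only starting event named for the 28-day outcome, and that the death rule directly follows the statement of the VFD endpoint. The natural reading is then a single clock from ICU admission, and nothing is mis-scored. Case A needs a second origin that the protocol never states. The exact day 0 could also be left to an analysis plan that is not at hand.

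Much of this stands. A reader might infer that the protocol contradicts itself and mis-scores deaths; the text does not show that. But the single-clock reading removes only the split between the two windows. It leaves the clock misaligned with entry and exposure, shortens the window for late-ventilated patients, and gives no origin to patients who never reach an ICU. Nor is this a detail merely left open: the protocol does fix an origin for the death rule, and it fits the protocol's own entry event badly.

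A reader might also infer a bias in favour of the one-tailed hypothesis, because "22% of ED patients and 18% of ICU patients had initial tidal volume settings >8 ml/kg PBW". The documents do not support that either:

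- The link is an unadjusted 0.114 ml/kg difference in 2014 data limited to volume control, whereas the planned model has hospital intercepts and patient covariates.
- Table 1 says nothing about tidal volumes in late-ventilated patients, who account for most of the error in case A.
- The ED/ICU gap may narrow once a 6 ml/kg default applies to all intubated patients.
- The sign reverses between the two cases.

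**Conclusion.** The point holds as one of definition. The death rule starts at ICU admission, entry and exposure start with ventilation, and day 0 of the VFD count is not stated. Either the two windows differ, or both start at the wrong event for this cohort. A patient without an ICU admission has no origin.

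The number affected cannot be computed from the documents. On the assumptions shown, case A changes about 0.1% of patients, and at the extreme about 1.1%. Case B mis-scores no death, but it shortens the window for every late-ventilated patient. The consequence for the estimated effect is probably small, and no direction of bias is established. Every figure on timing rests on assumed lags, shares and death risks. Nothing here changes the sample size. The point is minor, and the change is a nearly free improvement.

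**What to change.** Name one day 0, initiation of mechanical ventilation, in both places that define the outcome: Research Strategy for Specific Aims 1 and 2, and Primary Outcomes. Suggested text:

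> VFDs are counted over the 28 days from initiation of mechanical ventilation; patients who die within those 28 days are counted as having zero VFD.

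Both halves are needed. Moving the death rule alone would create a split if the count was meant to run from ICU admission.

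State which listed field supplies day 0, the intubation date or the "First Date of Ventilator Check". The listed death-timing field runs from the admission date, so recover the death date as admit date plus that difference and re-express it as days from the start of ventilation.

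The cost is a changed definition in two sections and one derived variable. No new data field is needed.

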- Measure compliance with the implementation of a computerized lung protective ventilation protocol at 11 Intermountain Healthcare hospitals

Specific Aim #1: Determine if the implementation of lung protective ventilation with a 6 ml/kg PBW tidal volume ventilation protocol on initiation of mechanical ventilation improves ventilator free days (VFDs) to day 28 (primary outcome), mortality, and secondary outcomes in **patients with acute respiratory failure requiring mechanical ventilation**.

- Process for Aim #1: Standardized management of mechanical ventilation and outcomes will be measured through electronic medical record data. A detailed plan on these metrics has been included (see research strategy for specific aims).
- **Hypothesis 1:** Deployment of the ventilation protocol will result in improvements in the number of VFDs to day 28, mortality, hospital discharge disposition, healthcare utilization and costs of care in patients with acute respiratory failure requiring mechanical ventilation.

Specific Aim #2: Determine if the implementation of lung protective ventilation with a 6 ml/kg PBW tidal volume ventilation protocol on initiation of mechanical ventilation improves VFDs to day 28, mortality, and secondary outcomes in **patients with ARDS requiring mechanical ventilation**.

- Process for Aim #2: Standardized management of mechanical ventilation for patients with ARDS and outcomes will be measured through electronic medical record data. A detailed plan on these metrics has been included (see research strategy for specific aims).
- Hypothesis 2: Deployment of the ventilation protocol in patients with ARDS will result in improvements in the number of VFDs to day 28, mortality, hospital discharge disposition, healthcare utilization and costs of care.

Specific Aim #3: Characterize protocol implementation of the high positive end expiratory pressure protocol (PEEP) and outcomes for mechanically ventilated patients with moderate or severe hypoxemia and ARDS.

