This is an observational quality improvement study comparing outcomes before, and after, implementation of a proven lung protective ventilation protocol in an electronic medical record system, iCentra, that will be implemented in phases across Intermountain Healthcare hospitals. A phased implementation with a twomonth washout period will be used to evaluate the primary outcome of interest, ventilator free days (VFDs) to 28 days. Secondary outcomes will include: use of the protocol by clinicians, compliance with protocol instructions, hospital discharge disposition, hospital, 30-day, and 90-day mortality, time to first ICU activity, hospital length of stay, ICU length of stay, heath care utilization, quality of life, and costs of care. As the iCentra electronic medical record is implemented at Intermountain Healthcare hospitals, clinicians will have the opportunity to use the computerized lung protective ventilation protocol, or to order mechanical ventilation settings independently. This is an observational study designed to measure how often the computerized lung protective ventilation protocol will be ordered, compliance with the instructions of the protocol, and clinical outcomes among patients who are managed with the protocol. Physicians may choose to use the protocol on intubated patients requiring mechanical ventilation or they may choose to order other specific mechanical ventilator settings.

A meta-analysis of mechanically ventilated patients without the acute respiratory distress syndrome (ARDS) reported that the cohort who received mechanical ventilation with initial tidal volumes between 6 and 10 ml/kg PBW had mean VFD of 21.9 (SD = 7.8). Using the distribution reported in the meta-analysis as the baseline for an a priori analysis, the current authors demonstrated that 3,900 patients would be sufficient to detect a 1.5-day increase in mean VFD with 80%

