Compliance with lung protective ventilation in the emergency department (ED)^{8,9} and ICU¹⁰ is not optimal. In the International LUNG SAFE study that included more than 550 ICUs around the world, mean tidal volume in patients with ARDS was 7.5 to 8.0 ml/kg PBW,¹⁰ and tidal volumes in patients with severe acute respiratory failure and PaO2/FIO2 ratios <300 was over 8 ml/kg PBW. In Europe, a prospective clinical trial is underway to determine whether tidal volumes of 4 to 6 ml/kg PBW improves outcomes as compared to 8 to 10 ml/kg PBW in patients with acute respiratory failure and ARDS.¹¹ Interestingly, the senior investigator of that study has used electronic decision support since 2006 in his medical and surgical ICU to recommend a default tidal volume of 6 ml/kg PBW on all intubated patients regardless of diagnosis.^{12,13}

In the previous studies of electronic decision support to implement lung protective ventilation, ^{12,13} the instructions were only purposed to provide the tidal volume calculated from 6 ml/kg of PBW when physicians and nurses were reviewing mechanical ventilation parameters. The computerized protocol that we propose herein to implement across Intermountain Healthcare provides specific instructions on management of mechanical ventilation with adjustment of respiratory rate, tidal volume, fraction of inspired oxygen (FiO₂), and positive end expiratory pressure (PEEP) with lung protective targets of a tidal volume of 6 ml/kg PBW and an inspiratory plateau pressure of < 30 cm H₂O. We will also provide a computerized weaning protocol. This complete computerized lung protective mechanical ventilation protocol will allow standardization of care across Intermountain for all aspects of management of mechanical ventilation.

Significance

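### The primary model estimates a slope on each patient's initial tidal volume, not the effect of deploying the protocol that Hypothesis 1, the design and the interim rule are about

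*Protocol*

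**What the plan says.** Specific Aim #1 takes VFDs to day 28 as its primary outcome and sets out to "Determine if the implementation of lung protective ventilation with a 6 ml/kg PBW tidal volume ventilation protocol on initiation of mechanical ventilation improves" it. Hypothesis 1 reads "Deployment of the ventilation protocol will result in improvements in the number of VFDs to day 28". Study Design opens with "This is an observational quality improvement study comparing outcomes before, and after, implementation of a proven lung protective ventilation protocol". The interim rule compares mean VFD after implementation with mean VFD before it, and Data Analysis justifies its one-tailed test by the expected benefit of the bundle.

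The model in Data Analysis is different. It is a mixed model with hospital random intercepts, quadratic time and patient covariates, and its exposure is initial tidal volume. The plan proposes to "measure the treatment as a continuous variable (rather than as a dichotomous indicator of whether the mechanically ventilated patient was cared for" after go-live, in order to allow for variable usual care. Equation 1 in Sample Size also defines x as initial tidal volume, with a coefficient of 1 to 2. The other tests named in Data Analysis are descriptive two-sample tests without hospital or time adjustment, so no adjusted model of deployment is stated.

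A third contrast also appears. Study Design speaks of "clinical outcomes among patients who are managed with the protocol", and Patient Selection divides patients into those managed with the protocol and those with physician-specified settings.

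**The concern.** Use of the protocol is voluntary: "Physicians may choose to use the protocol on intubated patients requiring mechanical ventilation or they may choose to order other specific mechanical ventilator settings". Tidal volume therefore varies by clinician choice before and after go-live, and a regression on it draws mainly on that choice. The result is an adjusted association. Its confounding is of unknown size and direction, and the promised covariates may remove only part of it.

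The package is also wider than initial tidal volume. According to Background it "provides specific instructions on management of mechanical ventilation with adjustment of respiratory rate, tidal volume, fraction of inspired oxygen" and PEEP, and "We will also provide a computerized weaning protocol". Under Significance, physicians may combine the component protocols as they wish. Any benefit from PEEP or weaning that does not track initial tidal volume is lost to the slope.

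At stake is the answer to Aim 1. A significant slope could be reported as a deployment effect when deployment did almost nothing, or a real deployment effect could be missed. The study could also stop at the interim on one contrast and report another at the end.

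**Working it through.** **Inputs from the protocol.** SD 7.8, ICC 0.10, one-sided 5%, 80% power, effects of 1, 1.5 and 2 days (Sample Size), so z = 1.645 + 0.842 = 2.486 (rounded down). Table 5 sums to 4,127 patients: 1,785 before and 2,342 after go-live. Table 1 (bin midpoints, n = 2,997) gives mean tidal volume 7.02 ml/kg, SD 1.27, and 603/2,997 = 20.1% at 6 ml/kg or less.

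**Assumptions (not in the protocol).** Uptake of 40, 70 or 100%; adopters set to exactly 6.0 ml/kg; SD of tidal volume 0.95 as a lower alternative. Residual SD s is 7.8, or 7.8 × √0.9 = 7.40 if 7.8 is the total SD.

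**1. The plan's own sample sizes.** After hospital effects, the go-live indicator on Table 5 has residual variance 0.0517 (quadratic time) or 0.0354 (categorical time). For a go-live term, N = (2.486 × s/effect)² / residual variance. For a slope, N = (2.486 × 7.8/(effect × SD of tidal volume))², with SD 0.9–1.27. For example, (2.486 × 7.8/1.5)² = 167.1, and 167.1/0.0517 ≈ 3,230.

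| Effect | Table 3, ICC 0.10 | Go-live, quadratic | Go-live, categorical | Slope, per ml/kg |
|---|---|---|---|---|
| 1 day | 8,500 | 6,550–7,280 | 9,570–10,640 | 230–465 |
| 1.5 days | 3,900 | 2,910–3,240 | 4,255–4,730 | 100–210 |
| 2 days | 2,300 | 1,640–1,820 | 2,390–2,660 | 60–120 |

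Table 3 is not reproduced exactly, and its simulated time effects are not given. Its order of magnitude fits a 0/1 exposure and not a tidal volume in ml/kg. As printed, a positive coefficient on tidal volume also means that larger volumes give more VFDs, against the hypothesis, unless x is coded as a reduction.

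**2. Where the slope's information comes from.** After projecting out hospital and quadratic time, the rollout supplies about 0.7%, 2.4% and 7.2% of the information at 40, 70 and 100% uptake (SD 1.27), or 1.1%, 3.8% and 12.2% (SD 0.95). The rest is within-period variation.

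**3. What a significant slope can mean (SD 1.27, s = 7.8).** Slope SE = 7.8/(√4,127 × residual SD of tidal volume). Mean fall = uptake × (7.02 − 6.0).

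| Uptake | Residual SD | SE | Detectable slope (2.486 × SE) | Mean fall, ml/kg | Implied shift (× 24) |
|---|---|---|---|---|---|
| 40% | 1.18 | 0.103 | 0.256 | 0.41 | 2.5 h |
| 70% | 1.06 | 0.115 | 0.285 | 0.71 | 4.9 h |
| 100% | 0.87 | 0.140 | 0.349 | 1.02 | 8.6 h |

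With SD 0.95 the shifts are 3.2, 6.2 and 11.1 hours. The planned effect is 1.5 × 24 = 36 hours.

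**4. A 1.5-day gain in every post-go-live patient, none of it through tidal volume.** The expected slope is 0.023, 0.050 and 0.106 day per ml/kg (SD 1.27) or 0.038, 0.080 and 0.179 (SD 0.95). Multiplied by the mean fall and 24, this implies 0.2–4.4 hours, with 8–25% power. The go-live term has SE 0.507–0.534, estimates 36 hours and has 88–91% power.

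**5. The same mean gain confined to patients set to 6 ml/kg.** The slope test has 79% power or more at 40–70% uptake and 19–25% at 100%, but it implies only 2.6–7.8 hours.

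**6. No uptake, hence no deployment effect (simulation, 400 runs).** If tidal volume is associated with VFDs at 0.5 day per ml/kg, the slope is significant in 100% of runs and the go-live term in 6%. With an assumed unmeasured confounder (correlation 0.3 with tidal volume, −1.5 days per SD) and no true effect, the figures are 98% and 4%.

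**The case against.** The tidal-volume exposure is a deliberate choice. The opening hypothesis expects initial tidal volumes to fall to target, the Aims are worded around tidal volume at initiation, and Equation 1 uses the same x. Variable usual care is real, as Table 1 shows. If the whole benefit runs through initial tidal volume and is unconfounded, the two models agree: with full uptake and a true effect of 1.5 days, simulation gave a slope of −1.48 days per ml/kg and a go-live effect of 1.52 days. Step 4 is the opposite extreme, and the uptake values are assumed.

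The go-live term is not clean either. It is non-randomised and coincides with the iCentra switch, staff education and new data mapping (Research Strategy for Aims 1 and 2, and for Aim 4). An assumed recording shift of 0.5 or 1.0 day would make it reject in about 24–26% or 59–63% of studies. If only adopters gain 1.5 days, its power is 63–67% at 70% uptake and 30–32% at 40%; in the latter case the slope test can do better (46–63%).

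All of this stands as a limit on what a go-live analysis can show. None of it turns the slope into a deployment effect. That conversion needs a benefit that is wholly linear in tidal volume, no residual confounding, and multiplication by the fall achieved, and the plan states none of these. Variable usual care supports a secondary dose-response analysis; it does not require dropping the deployment contrast.

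**Conclusion.** The concern holds and must be fixed. The mismatch between Hypothesis 1, the design and the interim rule on one side and the only primary model on the other is plain from the text and needs no assumption. The share of information in step 2 and the hours in steps 3 to 5 depend on the assumed uptake and tidal-volume SD, but across the whole range examined most of the slope's information is not the rollout. The comparison with Table 3 is supporting evidence only: it shows an order of magnitude, not which exposure was simulated.

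**What to change.** - Make a 0/1 post-go-live indicator the primary regressor. Exclude washout and classify every eligible patient by hospital and date, whether or not the protocol was ordered. Keep the hospital, calendar-time and patient covariate terms.
- Allow for hospital-by-period variation, in the model or as a sensitivity analysis.
- Keep the tidal-volume slope and the ordered/not-ordered comparison as secondary associations, and report initial tidal volume as a process outcome.
- Redefine x in Equation 1, rerun and restate Table 3, and reconcile Specific Aim #1, Study Design, Patient Selection, Sample Size and Data Analysis.
- State that the estimate is of the whole go-live package, including the iCentra switch. If feasible, check VFD extraction against charts in a sample before and after the switch.

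The work is wording, one model term, a rerun of the simulation, one variance term or sensitivity analysis and a limitation paragraph. Hospital and dates are already collected, so only the chart check needs new data.

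There is a price in power. With hospital intercepts only, one-sided power for an average 1.5-day rise at 4,127 patients is 88–91% (quadratic time) or 75–79% (categorical time). If 5–10% of the hospital variance is assumed to vary by month, ignoring it raises type I error to about 9–12%; modelling it gives power of 72–80% (quadratic) or 60–68% (categorical).
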